¹ Figure 1 represents the number of months of ART received by a patient. At the initial visit, the patient is given 1 month (30 days) of ART, so the first column represents those who were initiated on ART, given 1 month of medication and never returned. Patients are typically given monthly refills for at least the first year, so the number of months of ART corresponds to the number of ART clinic visits.

[figure not shown]

Table 1. Current status (as of March 2017) of a 12-month cohort of ART patients ages 15-21 who enrolled in ART between April 2015 and March 2016 in Akwa Ibom and Cross River states (n=2,043).

n	%	
602	29.5%	
9	0.4%	
63	3.1%	
22	1.1%	
15	0.7%	
1332	65.2%	
	602 9 63 22 15	602 29.5% 9 0.4% 63 3.1% 22 1.1% 15 0.7%

Anecdotal evidence collected during an information gathering trip in October 2016 for this study revealed that in-school youth, in particular, have a difficult time traveling to health facilities. Many SIDHAS staff and health facility personnel stated that many students in Nigeria attend boarding schools, and they often find it difficult to leave school to attend health care appointments. Students may not disclose their HIV status to teachers or other students, so leaving school for anything to do with their HIV infection can be challenging. Even among those YLHIV who live at home, going to health facilities and to meetings can raise questions for those to whom the YLHIV have not disclosed their HIV status. Therefore, SIDHAS is keen to work with YP ACTION to develop and test alternatives to existing strategies to identify additional tools to support better health outcomes among YLHIV.

Given the increasing access to and use of mobile phone technology in Nigeria, mHealth strategies have potential to meet the informational and social support needs of YLHIV who might not be able to participate or interested in in-person support groups. According to a survey conducted in 2014 by the Pew Research Center, 89 percent of Nigerians ages 18 and older own a cell phone, and phone ownership has been increasing at a dramatic rate over the past decade.³¹ A 2012 study conducted in Nigeria found that, at the time, more than half of females ages 12-30 years owned a phone and almost all of the girls and women who

Protocol: The Youth SMART study of an online support group intervention among YLHIV in Nigeria PHSC #1151489; Version 4.0; March 29,2019

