 - q027>today_bl AND latest follow-up date prior to transfer is missing
 t ltfu 90=9
- if **ltfu_90=9**
 - o ret_time_90=q028-today_b1

Missingness will be handled in the following way:

- If a follow-up date (i.e. **v7q044**) is missing (. or Jan 1 1990) and retained up to that point, retention must be assessed using the clinic visit date at which the follow-up date is missing. Consider retention time to be the visit date + 28 days as a conservative estimate of the follow-up time. Consider censored if retained up to that point.
- If a participant has died [died==1] but is missing date of death [q028] and appears to be retained throughout the entire study period, retention time is assessed based on the latest attended visit (i.e. v2q036), given that we do not know if participant died prior to the scheduled follow-up date.
- If a participant has transferred [transfer==1] but is missing date of transfer [q027] and appears to be retained throughout the entire study period, participant is categorized as transferred (ltfu_28/ltfu_60/ltfu_90==8) and retention time is assessed based on the latest available follow-up date (i.e. v7q044)
- If medical record data are incomplete towards the end of the study period (i.e. **latest_mre** falls before **today_el/today_el_approx**), then retention is assessed using **latest_mre** as the pseudo-endline date. Retention cannot be assessed into the future.
- If no visit data for participant during the study period or all visit dates for participant are missing during the study period (. or jan 1 1990), then retention time is missing and LTFU status is missing.
- We will generate a variable, conservative, to indicate whether participants have complete medical record data (conservative=1) or have a gap during the beginning of the study period conservative=.).

conservative=1 if (v1q036-today_bl)<=56 & v1q036!=.

conservative=. otherwise

Other variables for descriptive analysis of retention data

Other variables will be created to describe retention and clinic visits during the study period:

n_visits=number of clinic visits attended during the study period

• Code:gen n_visits=.

```
forvalues i=11(-1)1 {
replace n_visits=`i' if v`i'q036!=. & n_visits==. & ((v`i'q036<=today_el &
today_el!=.) | (v`i'q036<today_el_approx & today_el_approx!=.))
}
replace n visits=0 if v1q036==. | ( v1q036<today bl & v2q036==.)</pre>
```

n missed 28=Number of clinic visits missed by more than 28 days during the study period

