Code: egen n_missed_28=rowtotal(v2ltfu_28 v3ltfu_28 v4ltfu_28 v5ltfu_28 v6ltfu_28 v7ltfu_28 v8ltfu_28 v9ltfu_28 v10ltfu_28 v11ltfu_28)

mean_followup_mo=Mean months of follow-up time during the study period

• Code: forvalues i=1/11{

```
gen v`i'fu=v`i'followup if ((v`i'q036<=today_el & today_el!=.) |
(v`i'q036<=today_el_approx & today_el_approx!=.))
}
egen followup_total=rowtotal(v1fu v2fu v3fu v4fu v5fu v6fu v7fu v8fu v9fu
v10fu v11fu)
gen mean_followup=followup_total/n_visits
gen mean_followup_mo=floor(mean_followup/30.44)
replace mean_followup_mo=1 if mean_followup_mo==0</pre>
```

Timeliness of scheduled intervention activities

Timeliness of each scheduled intervention activity, including scheduled postings and group chats, will be calculated using Facebook group data from Grytics to evaluate the extent to which each group was implemented as planned. The difference between the scheduled date and the actual date will be calculated for each intervention activity; timeliness will be dichotomized with activities coded as timely if they occurred within one week of the scheduled time, and untimely if they occurred outside of this one-week window. The proportion of missing data will be reported.

High and low intervention engagement

Facilitators will be asked to identify the highest- and lowest-engaged participants in their Facebook groups. High and low engagement participants will be recruited at endline to participate in IDIs.

Social Support [MOS-SSS]¹

People sometimes look to others for companionship, assistance, or other types of support. How often is each of the following kinds of support available to you if you need it?

Factor	Item	Item
	no.	
Emotional/	1	Someone you can count on to listen to you when you need to talk
support	2	Someone to give you information to help you understand a situation
	3	Someone to give you good advice about a crisis
	4	Someone to confide in or talk to about yourself or your problems
	5	Someone whose advice you really want

	6	Someone to share your most private worries and fears with
	7	Someone to turn to for suggestions about how to deal with a personal problem
	8	Someone who understands your problems
Tangible support	9	Someone to help you if you were confined to bed
	10	Someone to take you to the doctor if you needed it
	11	Someone to prepare you meals if you were unable to do it yourself
	12	Someone to help with daily chores if you were sick
Affectionate support	13	Someone who shows you love and affection

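### The SAP rounds each participant's mean visit interval down to whole 30.44-day months, so a 60-day mean is reported as 1 month, and an unrecorded interval may lower that mean further

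*SAP*

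**What the plan says.** SAP section IV.C, under the sub-heading on other variables for describing retention data, builds the variable in four steps.

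- The intervals of visits 1 to 11 that fall within the study period are summed: "egen followup_total=rowtotal(v1fu v2fu v3fu v4fu v5fu v6fu v7fu v8fu v9fu" and so on to `v11fu`.
- The sum is divided by the visit count: "gen mean_followup=followup_total/n_visits".
- The result is turned into months: "gen mean_followup_mo=floor(mean_followup/30.44").
- Zeros are changed: "replace mean_followup_mo=1 if mean_followup_mo==0".

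The output is labelled "mean_followup_mo=Mean months of follow-up time during the study period". The denominator is described as "n_visits=number of clinic visits attended during the study period", and its code looks only at attended-visit dates (`q036`), not at next scheduled dates (`q044`). Each `v#fu` is copied from `v#followup`, which the SAP text does not define.

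The SAP's rules for survival-analysis retention, in the same section, expect some next scheduled dates to be absent. One rule covers a follow-up date that "is missing (. or Jan 1 1990) and retained up to that point", and it uses the visit date plus 28 days as the retention time.

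SAP section VI, Objective 1, presents the variable descriptively by intention-to-treat arm. It sits alongside the number of visits and the number missed by more than 28 days, for participants with `conservative=1`, a non-missing `ltfu_28` and a non-zero `ret_time_28`.

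For the length of a month of supply, footnote 1 of the protocol's Background says: "At the initial visit, the patient is given 1 month (30 days) of ART".

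**The concern.** A floor on a 30.44-day month works badly with schedules made of 30-day or 28-day months. Each whole multiple falls just short of the next integer and loses a month. The SAP's reset of 0 to 1 repairs this for one-month spacing only. Separately, the numerator and denominator need not cover the same visits, because one sums intervals and the other counts visit dates.

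The variable matters as context for the primary result. A participant can be late only against a scheduled date, and the primary survival analysis stops at 270 days. Spacing of 30 days gives about 270/30 = 9 scheduled dates in that time, and spacing of 90 days about 270/90 = 3. Of the three items in this table, this is the only direct description of spacing. The number of visits reflects it indirectly and also depends on attendance.

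**Working it through.** The documents state no numerical value for this variable, so there is no figure of the plan's own to reproduce. The check applies the SAP code as written.

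**Inputs**

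- Month length 30.44 days, floor, and 0 reset to 1: SAP section IV.C.
- Row total over `v1fu` to `v11fu`: SAP section IV.C. Stata's `egen rowtotal`, used without its missing option, counts a missing value as 0.
- Denominator `n_visits`, set from visit dates: SAP section IV.C.
- One month of supply is 30 days: protocol Background, footnote 1.
- Assumption: `v#followup` is the days from a visit to the next scheduled date. The division by 30.44 implies days. The rest is inferred from the SAP calling `q044` the follow-up date.

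**Step 1: the floor.** Reported months = floor(m / 30.44), with 0 changed to 1, where m is the participant's mean interval in days.

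| m (days) | m / 30.44 | floor | reported |
|---|---|---|---|
| 28 | 0.920 | 0 | 1 |
| 30 | 0.986 | 0 | 1 |
| 56 | 1.840 | 1 | 1 |
| 60 | 1.971 | 1 | 1 |
| 62 | 2.037 | 2 | 2 |
| 84 | 2.760 | 2 | 2 |
| 90 | 2.957 | 2 | 2 |
| 92 | 3.022 | 3 | 3 |
| 120 | 3.942 | 3 | 3 |
| 180 | 5.913 | 5 | 5 |

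The mean must reach 2 × 30.44 = 60.88 days to be reported as 2, and 3 × 30.44 = 91.32 days to be reported as 3. Everything below 60.88 days is reported as 1. Below 30.44 days the reset raises the value (28 days is 0.92 month, reported as 1).

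**Step 2: attended visits with no recorded interval.** m = (sum of recorded intervals) / (all attended visits).

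- 90, 90, missing: 180/3 = 60 days, and 60/30.44 = 1.97, reported as 1. The mean of the recorded intervals is 180/2 = 90 days, or 2.96 months. The floor alone would report 2, so the denominator costs the second month.
- 62, 62, 62, 62, missing: 248/5 = 49.6 days, reported as 1. The recorded mean is 62 days, which the same code would report as 2.
- Four attended visits, all intervals missing: 0/4 = 0, floor 0, reset to 1. A participant with no interval data is reported as 1 month.

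Visits never attended do no harm, because they add 0 to the sum and are not in `n_visits`.

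**Step 3: the placeholder date.** The SAP treats 1 January 1990 as a code for missing. If it were not set to missing before `v#followup` is formed, a visit in this trial (enrolment from September 2018 in the protocol timeline) would contribute a negative interval of more than 28 years, not zero. The text does not show whether this recoding is done for this variable.

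**The case against.** The case for leaving the code alone has real content.

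- **Completed months is a known convention.** That is fair in general. Here, though, the code departs from its own convention by turning 0 into 1, and it then leaves the same shortfall at 2, 3 and 6 months of 30 days.
- **Visits are usually monthly.** The protocol says so in the Background footnote, under sampling and recruitment, and under the retention measure. For 28- or 30-day spacing the code returns 1, which is sensible. This stands. The documents report no schedule of 60, 90 or 180 days, so the distortion may touch few participants.
- **The missing-as-zero effect is conditional.** The 28-day substitute for a missing follow-up date is written for retention time. If it also feeds `v#followup`, those intervals are not missing. The text does not settle this, so the effect is a possibility that depends on an undefined variable.

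A reader might also infer more than the documents support.

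- *Every participant with some 60- or 90-day intervals is a month too low.* The floor acts on each participant's mean over all visits, so the figures hold only when that mean takes those values. Means of 62 or 92 days are reported as 2 and 3.
- *The code always understates spacing.* The reset raises means below 30.44 days.
- *The table conceals a difference between arms.* The same code applies to both arms, and nothing in the documents says that spacing differs by arm in this individually randomised trial. It could hide such a difference, but that is all.
- *The retention result is biased.* The Kaplan-Meier estimates, the log-rank test, the `ret_time` variables and the specified regression models do not use this variable.

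**Conclusion.** The point holds in a limited form. Followed exactly, the SAP reports a participant mean of 60 days as 1 month, 90 days as 2 and 180 days as 5. It cannot separate 30-day from 60-day spacing. Where an attended visit has no recorded interval, the mean is lowered further, and a participant with attended visits but no intervals at all is shown as 1 month.

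This rests on reading `v#followup` as days from a visit to the next scheduled date. The second part also requires that no substitute date fills the missing intervals. Per participant, the floor takes off less than one month, and the denominator effect grows with the share of attended visits lacking an interval. The overall size cannot be computed, because the documents give neither the distribution of visit spacing nor a rate of missing next dates. The consequence is confined to one item in a descriptive table, and no primary or secondary test changes. It is a low-priority correction, but worth making because the stated rule gives a wrong number and is cheap to repair.

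**What to change.** - Define `v#followup` in the SAP (start date, end date, unit), and say whether the 28-day substitute applies to it.
- Set 1 January 1990 placeholders to missing before any interval is computed.
- Replace the row total over `n_visits` with `rowmean` of `v1fu` to `v11fu`. These are already limited to visits in the study period, and `rowmean` averages only the non-missing ones. A participant with no recorded interval then stays missing.
- Drop the floor and the 0-to-1 reset. Report the mean or median interval in days, or in unrounded months. Rounding to the nearest month is not a good substitute, since a mean of 45 days on a 30-day month (45/30 = 1.5) would become 2.
- Show by arm how many participants contribute and how many attended visits lack an interval, so that the size of the missing-date problem can be seen.

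The cost is a few lines of Stata and a sentence or two in the SAP. No new data are needed, and no other analysis is affected.

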In addition to clinic records, at the end of the study, personal contact information, including phone number and home address, gathered during study enrollment will be used to trace participants who do not return for endline interviews to determine if the person has transferred care elsewhere. If the person has transferred care, we will request the SIDHAS staff, who have access to clinic records in SIDHAS-supported facilities, to verify the patient has attended his/her 12-month appointment within the 3 -month timeframe.

Objectives 2 and 3:

- 2. To examine the effect of the online support group on social support, HIV knowledge and treatment literacy, and ART adherence among YLHIV.
- 3. To test the potential mediating effect of social support on the relationship between the intervention and primary outcome.

Social support: To measure social support, we will use the Medical Outcomes Study – Social Support Survey (MOS-SSS).⁴¹ This scale, developed in the early 1990's, has been used extensively in a number of different countries and with a variety of health outcomes, including HIV in China, Ireland, the US and in Ghana.⁴²⁻⁵⁰ The MOS-SSS is a 19-item scale that covers the dimensions of emotional, information, affectionate and tangible social support in addition to positive social interaction.

Adherence to anti-retroviral treatment: Adherence to ART will be measured through self-reported measures in the structured questionnaire of treatment adherence and challenges with taking medication as prescribed. In the study, we will measure self-reported adherence using the AIDS Clinical Trials Group adherence measure (AACTG baseline: http://caps.ucsf.edu/uploads/tools/surveys/pdf/2098.4186.pdf). This validated measure has been widely used to measure adherence for research purposes. We will also extract viral load and CD4 cell count data from patient medical records.

HIV Knowledge and Treatment Literacy: A set of 15 knowledge-based questions covering HIV transmission, diagnosis, treatment, and treatment monitoring have been developed based on topics covered in the Positive Connections curriculum. Each item is scored 1 if answered correctly and 0 if answered incorrectly. A total knowledge score is calculated based on the sum of the items with a possible range of 0 to 10.

Additional psycho-social measures

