 - [if yes] How often did this happen? (Rarely [1-2 times], Sometimes [3-10 times], Often [more than 10 times])
- Did you or any household member go a whole day and night without eating anything at all because there was not enough food
 - [if yes] How often did this happen? (Rarely [1-2 times], Sometimes [3-10 times], Often [more than 10 times])

Following scoring guidelines, a new variable will be created for each question with the following response options:

- Indicated that this type of food insecurity did not happen (variable=0)
- "Rarely" or "sometimes" (variable=1)
- "Often" (variable=2)

An aggregate score will be created by summing the three new variables. The aggregate score will have a minimum score of 0 and a maximum score of 6. Results at each time point will be represented as mean aggregate score at each time point. We will also present the proportion of participants in each of the following household hunger categories as per the HHS scoring guide:

- Aggregate score 0-1: Little to no hunger in household
- Aggregate score 2-3: Moderate hunger in household
- Aggregate score 4-6: Severe hunger in household

Adherence

Adherence will be dichotomized at baseline and endline (adh_bl,adh_el) based on self-reporting having missed one more medication dose in the past 3 days (q422).

Code:

gen adh_el=.

⁷ Information on scoring the HHS is available from: https://www.fantaproject.org/sites/default/files/resources/HHS-Indicator-Guide-Aug2011.pdf

replace adh_el=1 if if q420==1 | q420==2 | q420==3 | q421==1 | q421==2 | q421==3 | q422==1 | q422==2 | q422==3 | q422==4 | q422==5; 0 otherwise

replace adh_el=0 if adh_el==. & (q420==4 | q420==5 | q420==6 | q421==0 | q422==0)

VL suppression

A dichotomous variable, vl_sup, will be created for each VL measurement instance to indicate virologic failure following the standard definition of virologic suppression being <1,000 cp/mL. The variable will be missing for any instances where VL measures were not available.

HIV knowledge and treatment literacy

HIV knowledge and treatment literacy will be assessed using a set of fifteen true/false questions [q226 – q240] administered at baseline, midpoint, and endline. For each knowledge question, a new variable will be created to more easily quantify correct responses and will be coded as 1 if a correct response was given, and 0 if an incorrect answer, "don't know" response, or refusal was given. For example:

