For adherence and viral suppression at endline, both of which will be dichotomized, we will conduct chisquare tests. We will also explore associations between treatment exposure and secondary outcomes using multiple linear regression models:

1. Social support

Model:	Multiple Linear Regression
Outcomes:	Change in social support score from baseline to endline (ss_avg_chng, individual sub- scales)
Exposures:	Study group (intervention v. comparison)
Covariates:	Age, sex, education at baseline, depression score at baseline, social isolation score at baseline

2. HIV knowledge/treatment literacy

Multiple Linear Regression Model:

Analysis Plan: Using Social Media to improve ART Retention and Treatment outcomes among youth living with HIV in Nigeria - The Youth SMART study

Outcomes: Change in knowledge score from baseline to endline (know chng)

Study group (intervention v. comparison) Exposures:

Covariates: Age, sex, education at baseline

3. Self-reported adherence

Model:	Multiple Logistic Regression
Outcomes:	Adherence at endline
Exposures:	Study group (intervention v. comparison)
Covariates:	Age, sex, education at baseline, household hunger score at baseline, time on ART at baseline, social support sub-scales, adherence at baseline

4. Viral load

Model:	Multiple Linear Regression
Outcomes:	Viral load at endline
Exposures:	Study group (intervention v. comparison)
Covariates:	Age, sex, education at baseline, household hunger score, adherence, time on ART at baseline, social support sub-scales

We will check that the following assumptions of multiple regression are met:

- Independence of observations (i.e. independence of residuals) ٠
- Linear relationships between dependent variable and each independent variable, and between dependent variable and the independent variables collectively. Method: Scatterplots
- Homoscedasticity variance does not change along line of best fit. Method: Plotting studentized • residuals against unstandardized predicted values
- No multicollinearity. Method: Inspect correlation coefficients and VIF values •
- No significant outliers, highly influential points, etc. Method: Exploratory data analysis
- Normal distribution of residuals. Method: Histogram with normal curve fitted, and normal p-plot of residuals

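### The SAP defines the self-reported adherence outcome one way in its text and another in its code, and gives the value 1 to missed doses in an unlabelled variable named for adherence.

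*SAP*

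**What the plan says.** ART adherence is a named secondary outcome in both documents. The protocol (Measures, Objectives 2 and 3) names only the instrument: "we will measure self-reported adherence using the AIDS Clinical Trials Group adherence measure". Its analysis section adds that adherence will be dichotomized and compared by chi-square test, but gives no rule. The SAP's section IV.C is therefore the only operational definition.

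- **Text.** Adherence is dichotomized at baseline and endline "based on self-reporting having missed one more medication dose in the past 3 days (q422"). Only q422 is named. The text does not say which category takes the value 1.
- **Code for 1.** "replace adh_el=1 if if q420==1 | q420==2 | q420==3 | q421==1 | q421==2 | q421==3", continuing with "q422==1 | q422==2 | q422==3 | q422==4 | q422==5; 0 otherwise".
- **Code for 0.** "replace adh_el=0 if adh_el==. & (q420==4 | q420==5 | q420==6 | q421==0 | q422==0").
- **Use.** SAP section VI, Objective 2, applies a two-sided chi-square test at alpha 0.05 to endline adherence. It then explores a logistic model whose outcome is labelled "Adherence at endline", with baseline adherence as a covariate. Adherence is also a covariate in the viral load model.
- **Neighbouring variable.** `vl_sup` is created "to indicate virologic failure following the standard definition of virologic suppression being <1,000 cp/mL".

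**The concern.** There are three linked problems.

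1. **Items.** The text rests on one item and the code on three. A participant with no missed dose on q422 can still be coded 1 through q420 or q421, so the two rules can give different proportions, effect sizes and p-values. The outcome is self-reported in an open-label trial, so the definition should not be left to be settled after data are seen.
2. **Direction.** For q422, 1–5 goes to 1 and 0 goes to 0, so 1 marks a missed dose in a variable named for adherence. Other created variables, such as care status at endline, the depression categories and the AUDIT-C risk levels, list what each value means. This one does not.
3. **Missing answers.** The trailing `0 otherwise` and the following line treat participants with no answers differently. These participants are to be expected: the SAP's rule for retention at endline already provides for people with no endline interview.

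**Working it through.** The documents give no rate, effect size or power for adherence, so there is no figure to reproduce. The wording and response codes of q420–q422 are not given either. The check runs the printed logic over all answer patterns and then uses assumed rates.

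**Step 1: the two rules over all patterns.** Take q420 = 1–6 or missing (7 states), q421 = 0–3 or missing (5) and q422 = 0–5 or missing (7). That gives 7 × 5 × 7 = 245 patterns. The text rule is 1 if q422 ≥ 1, 0 if q422 = 0, and missing if q422 is missing. The code is run here without `0 otherwise`.

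| q422 | Patterns | Text rule | Code gives 1 | Code gives 0 | Code gives missing |
|---|---|---|---|---|---|
| 1–5 | 175 | 1 | 175 | 0 | 0 |
| 0 | 35 | 0 | 27 | 8 | 0 |
| missing | 35 | missing | 27 | 7 | 1 |

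When q422 = 0, the code returns 0 only if q420 is 4–6 or missing (4 states) and q421 is 0 or missing (2 states): 4 × 2 = 8, and 35 − 8 = 27. These are counts of possible patterns, not expected shares of participants.

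**Step 2: effect of the item set on the test.** Assume 250 per arm all answer, and q422 shows a missed dose in 30% of control (75) and 20% of intervention (50).

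- q422 only: χ² = 500 × (75 × 200 − 175 × 50)² / (250 × 250 × 125 × 375) = 6.67, p = 0.0098.
- Pooled, if q420 or q421 flags a further 20% of the rest in each arm: control 0.30 + 0.70 × 0.20 = 0.44 (110); intervention 0.20 + 0.80 × 0.20 = 0.36 (90). χ² = 500 × (110 × 160 − 140 × 90)² / (250 × 250 × 200 × 300) = 3.33, p = 0.068.

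More widely, if 10–30% report a missed dose on q422 and the other items flag 0–30% of the rest, the pooled missed-dose rate lies between 10% and 0.30 + 0.70 × 0.30 = 51%.

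**Step 3: effect of coding direction.** The q422-only table from step 2 corresponds to 70% adherent in control and 80% in intervention.

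- Odds ratio for adherence: (200 × 75) / (50 × 175) = 1.71.
- Odds ratio for the variable as coded: 1 / 1.71 = 0.58.
- χ² = 6.67 and p = 0.0098 under both codings.

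Other assumed pairs behave the same way: 80% against 88% gives 1.83 or 0.55 with p = 0.0147 both ways, and 50% against 60% gives 1.50 or 0.67 with p = 0.025 both ways.

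**Step 4: missing answers.** With all three items missing, `0 otherwise` gives 0 (no missed dose), while the next line alone leaves the value missing. If `0 otherwise` is applied, nobody remains missing for the next line to act on. The derived variable then shows no missingness, so these participants escape both the complete-case rule and the 5% imputation trigger (SAP section IV.B, Missing data) wherever those are applied to `adh_el` and not to its items.

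**The case against.** The text itself bases the split on a missed dose, so text and code agree on the event for q422. The planned test is two-sided and indifferent to coding. The models are introduced as exploratory, and an analyst who knows what 1 means will report them correctly. All of this stands. It rules out inferring that the adherence effect would be reported in the wrong direction: only the odds ratio inverts, and only if 1 is read as adherent.

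Four other inferences are tempting and unsupported.

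- **That the code is the wrong definition.** The documents do not say whether text or code was intended. For q420 and q421, even the reading of 1–3 as missed doses is inferred from their place in the same condition.
- **That pooling can only lower measured adherence.** This holds among people who answered q422. The second code line also admits people who left it blank. As an assumed example, of 100 people 40 answer q422 and 20 of them missed a dose; the other 60 leave it blank with q421 = 0; nobody else is flagged. Adherence is 20/40 = 50% on q422 alone and 80/100 = 80% pooled.
- **That non-responders will certainly count as adherent.** The code starts from missing, and the line assigning 0 would be pointless if everyone else were already 0. `0 otherwise` may be a stray annotation. The first line would not run anyway, because of `if if`. What is shown is a conflict that the programmer must resolve.
- **That `vl_sup` is reversed.** No code for it is printed, it is tested by chi-square, and the viral load model uses viral load itself. The name and threshold point to suppression. Only the word failure is ambiguous.

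The objection does not reach the item mismatch, which changes who is classified and so can change the main test.

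**Conclusion.** The point holds as an inconsistency in the only operational definition of a named secondary outcome. The one-item text and the three-item code disagree on 27 of the 35 patterns with q422 = 0. The code also assigns a value to 34 (27 + 7) of the 35 patterns with q422 missing, where the text rule gives none. The effect on the trial's result cannot be sized without the item wording and response distributions. Under the assumed rates in step 2, the choice of items moves p across 0.05.

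The unlabelled coding is a reporting risk confined to the exploratory odds ratio, which becomes its reciprocal if read under its label. The missing-data conflict matters in proportion to the number of participants with none of the items answered, which the documents do not give. The primary outcome is not touched.

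**What to change.** Before analysis, amend SAP section IV.C as follows:

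- Choose one item set and recall period, use it in both text and code, and print the wording and response codes of the items used.
- Apply the same rule to `adh_bl` and `adh_el`. No baseline code is printed, although baseline adherence is a covariate.
- Code and label 1 = no missed dose, 0 = any missed dose, so that the label in Objective 2 is true.
- Delete `0 otherwise`, leave the value missing when the defining items are missing, and correct `if if`.
- State that `vl_sup` = 1 means below 1,000 copies/mL and remove the word failure.

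The cost is a few lines of SAP text and code. No new data are needed. If the item set is chosen after outcome data have been seen by arm, that should be disclosed and both versions reported.
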